SELF-MANAGEMENT APP FOR PATIENTS WITH LEFT VENTRICULAR ASSIST DEVICES

STUDY PROTOCOL & STATISTICAL ANALYSIS

[name]

University of Michigan
Johns Hopkins University

NCT # ***NCT03049748***

Purpose

This study aimed to obtain preliminary efficacy data of using a mobile phone application (VAD Care App)¹ as a self-management tool in patients with left-ventricular assist devices (LVAD). The specific aim was to evaluate the effects of the app on the patient's (1) self-efficacy and (2) adherence to the LVAD care regimen; (3) complications; (4) overall health status, and (5) quality of life.

Study Design

Pilot randomized control trial. Measurements completed at baseline (T0) and months 1 (1), 3 (T2), and 6 (T3) post-hospital discharge.

Sample and Setting

This study recruited a total of 68 patients with newly implanted, non-pulsatile flow durable LVADs and from four VAD Centers in the Midwest and Northeast regions in the United States. The study was implemented in inpatient and outpatient settings of the hospitals.

Study Procedure

Recruitment and screening. A trained clinical research coordinator (CRC) conducted all recruitment and screening of study participants. Recruitment and obtaining informed consent occurred in each hospital's inpatient setting. A screening checklist based on the study inclusion and exclusion criteria (table insert) was used. Since cognitive impairment is common in heart failure, we used the 11-item Mini-Mental State Exam (MMSE) as a screening tool. The MMSE is a valid, reliable, and widely used cognitive screening tool across care settings and conditions worldwide. A score of less than 24 in the MMSE denotes cognitive impairment.^{2,3} Participation in this study also required a dedicated caregiver, a customary practice in the participating VAD centers.

Patients	
Inclusion	
• First-time LVAD implant
	
• 21 to 80 years of age
	
• 6th grade education or higher
	
• Can read and understand English
	
• Planned hospital discharge within a week of enrollment
	
• Completed LVAD care training
Exclusion	
• Blindness
	
• Inability to or refuse to use a smartphone
	
• Cannot hear alarms, and/or
	
• Cognitively impaired documented in the medical record of an MMSE score <24

Randomization. Upon confirming eligibility to participate, patients were randomized in the study using a sample randomization procedure. Randomization, prepared by a statistician, using a computer-generated 1:1 allocation of patients to either a control group or an intervention group. A coding scheme (ID#, site, study group), matching with the master list of patient names, as study participant identification was developed. Personally, identifiable data and group

assignments kept separately from other study data. Each site kept the study data in a locked cabinet *and* a password protected and encrypted desktop computer.

- **Control group:** Patients received packets containing study instructions and self-administered questionnaires. They also received the *usual care* throughout the study (6 months). Usual care is defined by the routine outpatient care customary to each VAD center. Many VAD Centers in the US share a similar approach to managing LVADs in outpatient clinics with routine follow-up care and as needed educational support (LVAD care) for patients/caregivers provided by specialized VAD nurses (RNs/NPs). Patients in the control group used the usual LVAD self-management process consisting of the utilization of LVAD system operation manuals and videos and logs for daily care, self-monitoring, and reporting to any of the outpatient VAD RNs/NPs. It is also a common practice for VAD Centers to require patients and/or caregivers to bring their LVAD care logs during routine clinic visits.
- **Intervention group:** Intervention patients performed LVAD self-management (assisted by caregivers as needed) as directed by the VAD Care App¹ and supported by VAD RNs/NPs throughout the process. The app provided the patient with directions in completing the tasks and procedures required for daily LVAD care and management. It also provided an efficient channel of communication between RNs/NPs, patients and/or caregivers for interventions related to abnormal results (e.g., low LVAD flow), making recommendations to correct a deficit in knowledge and skills of LVAD self-management and to address other LVAD care-related issues rapidly. Additionally, the app notified the RNs/NPs with text messages when a patient did not complete self-management for two consecutive days. In addition to receiving the *usual care*, patients in the intervention group had:
 - a. Completed a study protocol training a day before discharge. First, the CRC downloaded the VAD Care App¹ into an iOS or an Android-compatible smartphone owned by the participant or provided by the study team. Second, the CRC trained the patient and caregiver in the use of the app. Third, the CRC asked the patient and caregiver to demonstrate the use of the app at least twice to ensure proficiency in using the app.
 - b. Received an intervention package consisting of study instructions, self-administered questionnaires, and smartphones with the app ready for use at home.
 - c. Used the app daily for a total of 6 months post-implantation hospital discharge. As prompted by the app, the patient and/or caregiver will implement the LVAD care regimen.
 - d. Completed an "*LVAD knowledge and skill review and evaluation*" at week 1, and months 1 and 5 to facilitate LVAD care self-efficacy and adherence. This review and evaluation were conducted by the VAD RNs/NPs during clinic visits or delivered via a video chat.

Data Collection. Data were collected at baseline (1-2 days before hospital discharge) and 1, 3, and 6 months after implantation hospitalization discharge. Approaches for data collection included reviews of a patient's healthcare/medical record, completion of self-administered questionnaires, and face-to-face interviews. The following data collection tools were used:

- **Demographic and Clinical Profiles.** Common demographic data such as age, sex, race, education, and health history collected from informants (patients and/or caregivers). Clinical profiles included LVAD indication (implant strategy), model, and other pertinent clinical data, including comorbidities and risk stratification in advanced heart failure (INTERMACS Classifications).³ The Charlson Comorbidity Index (CCI), which evaluated 17 different comorbidities assigned to various weights (scores), were also employed. The CCI is a valid and reliable measurement instrument that is widely used for evaluating comorbidity indexes in cardiovascular, cardiac surgery, and LVAD patients.^{4,5}
- **LVAD Care Self-Efficacy** was measured with a 20-item LVAD Patient Self-Efficacy Scale, used to assess a patient's confidence in managing the challenges presented by the daily LVAD care regimen. The instrument employs a 6-point rating scale ranging from 0 (*not confident at all*) to 5 (*extremely confident*), with standardized sum scores ranging from 0 to 100. High sum scores indicate higher confidence in one's ability to manage the complexity of the regimen. The validity and reliability of the instrument were already established by factorial and convergent validity with a Cronbach's alpha coefficient of 0.92.⁶⁻⁹
- **Adherence** to the LVAD care regimen was measured with the 9-item LVAD Patient Home Management Adherence Scale, used to assess the degree of the patient's consistency in completing the daily LVAD care. The instrument employs a 6-point rating scale, ranging from 0 (*never*) to 5 (*all the time*), with standardized sum scores ranging from 0 to 100. High sum scores indicate high adherence to the regimen. The validity and reliability of the instrument were also established by factorial and convergent validity with a Cronbach's alpha coefficient of 0.95.⁶⁻⁹
- **Complications and Hospital Readmission.** Two separate forms were created for capturing characteristics and frequency of LVAD-related complications and unplanned hospitalization through a monthly review of the patient's medical record(s) and interviews of patients and/or caregivers. These forms consisted of a checklist and tables format, a commonly used approach for collecting complications and healthcare utilization/hospital readmission episodes in heart failure.¹⁰
- **Quality of Life** was measured with the Kansas City Cardiomyopathy Questionnaire (KCCQ). This 23-item instrument used to assess several health-related QOL domains, including physical function, symptoms, social function, among others. The instrument employs a 6-point Likert response scale with sum

scores ranging from 0 to 100. High sum scores indicate better quality of life. The validity, reliability, and sensitivity of the KCCQ have been well established in patients with heart failure and LVADs worldwide.¹¹⁻¹³

Data Analysis. All data management and statistical analyses performed with REDCap and SAS.^{14,15} Study data were checked for quality and completeness. Data were also checked to ensure that assumptions were met before performing statistical analyses. Descriptive statistics and graphical displays used to summarize the data by the study group. Continuous variables summarized with medians and IQR or means and standard deviations, depending on the distribution. Categorical variables were summarized using percentages and frequencies. Differences in the study group's outcome variables were compared for each period (T0, T1, T2, and T3) with Mann Whitney U tests and chi-square tests set at 0.05 level of significance. Confidence intervals (95%) provided with the summary statistics as well as model estimates and effect size estimates for the next stage of this pilot.

REFERENCES

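### Baseline risk (INTERMACS class, Charlson index) is collected, but no named analysis uses it; a prespecified adjusted model for complications would be a minor, cheap improvement

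*Combined protocol and SAP*

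**What the plan says.** - **Study aim (Purpose).** Complications are the third of five targets: "adherence to the LVAD care regimen; (3) complications; (4) overall health status, and (5) quality of life". Readmission is not listed there.
- **Baseline risk (Data Collection, Demographic and Clinical Profiles).** The clinical profile covers LVAD indication, device model and other data, "including comorbidities and risk stratification in advanced heart failure (INTERMACS Classifications"). It adds: "The Charlson Comorbidity Index (CCI), which evaluated 17 different comorbidities assigned to various weights (scores), were also employed".
- **Outcome (Data Collection, Complications and Hospital Readmission).** Two forms are used for "capturing characteristics and frequency of LVAD-related complications and unplanned hospitalization through a monthly review" of records, together with interviews. No event rate is given, and no per-patient analysis variable is defined.
- **Allocation (Randomization).** It states that "patients were randomized in the study using a sample randomization procedure", "using a computer-generated 1:1 allocation of patients to either a control group or an intervention group". The word before randomization may be a slip for simple. Either way, no stratification or blocking by risk or site is described.
- **Analysis (Data Analysis).** Outcomes are "compared for each period (T0, T1, T2, and T3) with Mann Whitney U tests and chi-square tests" at the 0.05 level. Neither risk measure appears in this section. It does say that data are summarized by study group, and that 95% confidence intervals will accompany model estimates and effect sizes meant for the next stage. It names no model, outcome or covariate for those estimates.

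**The concern.** The questionnaire scales have a T0 value that shows where each arm started. Complications and unplanned hospitalizations are counted after discharge and have no T0 value of their own, so any account of starting risk must come from other baseline data. The plan collects two recognized risk summaries and then names only tests that cannot use them.

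If sicker patients happen to fall more often in one arm, part of the difference in complications reflects that allocation rather than the app. The effect sizes are meant to inform the next stage, so a displaced estimate could be carried into its planning. Leaving the model undefined also means that any adjustment might be chosen after the imbalance has been seen.

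**Working it through.** The documents give no power, event rate, SD or derivation of the sample size, so there is no planned figure to reproduce. The check is of the size of the problem.

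**Inputs.** From the documents: "This study recruited a total of 68 patients with newly implanted, non-pulsatile flow durable LVADs", allocated 1:1. Inferred: 68 / 2 = 34 per arm. Assumed: risk ratio per SD of the index (1.3 to 1.6), mean event count 1 per patient, overdispersion 0.5, no dropout.

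**1. Chance of an imbalance in one index.** The SD of the standardized difference is sqrt(2/34) = 0.2425.
- P(above 0.25 SD) = 2[1 − Φ(0.25/0.2425)] = 30.3%
- P(above 0.5 SD) = 2[1 − Φ(0.5/0.2425)] = 3.9%
- P(0.3 to 0.45 SD) = 2[Φ(1.856) − Φ(1.237)] = 15%

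If allocation was truly simple, an exact 34/34 split has probability 9.6%, and the 95% range for one arm is 26 to 42. At 26/42 the SD is sqrt(1/26 + 1/42) = 0.2495 and P(above 0.25 SD) is 32%, so the inferred arm size matters little.

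**2. What carries over.** With risk ratio r per SD and imbalance d, the event rate ratio with no app effect is r^d.

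| r per SD | d = 0.25 | d = 0.5 |
|---|---|---|
| 1.3 | 1.07 | 1.14 |
| 1.5 | 1.11 | 1.22 |
| 1.6 | 1.12 | 1.26 |

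In simulation the SD of the log rate ratio was about 0.33, so a 95% interval spans a factor of exp(1.96 × 0.33) = 1.9 either way. Every shift in the table lies inside that.

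**3. False-positive rates.** Simulated trials with no app effect compared a rank test with a rank-based covariate-adjusted test. There were three runs at 1.6-fold, of 20,000 to 40,000 trials per scenario; not every run reported every cell.

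| Risk per SD | Allocations | Unadjusted | Adjusted |
|---|---|---|---|
| 1.6 | all | 5.0% | 5.0-5.1% |
| 1.6 | imbalance 0.3-0.45 SD | 5.8-6.4% | 4.7-5.4% |
| 1.6 | imbalance above 0.5 SD | 10.1% | 4.7-5.4% |
| 1.3 | imbalance 0.3-0.45 SD | 5.5% | 5.2% |
| 1.3 | imbalance above 0.5 SD | 7.5% | 5.2% |

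The 0.3-0.45 SD band holds about 15% × 20,000 = 3,000 trials in the smallest run. The Monte Carlo standard error there is sqrt(0.058 × 0.942 / 3,000) = 0.4 points, so the spread between runs is noise.

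**4. Precision.** At 1.6-fold, power for an assumed halving of events was 41.6% unadjusted and 43.9% adjusted.

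**5. Cross-check with a yes/no outcome.** Assumptions: a binary risk factor with 50% prevalence, a mean event rate of 40%, and strata differing by 10, 20 or 30 points. An imbalance of 20 points or more occurs in 11% of allocations.
- A 20-point imbalance shifts the risk difference by 0.20 × 10, 20 or 30 = 2, 4 or 6 points. The 95% half-width is 22-24 points at event rates of 30-50%, for example 1.96 × sqrt(2 × 0.5 × 0.5 / 34) = 0.238.
- Error given an imbalance of 20 points or more is 5.6%, 7.0% and 9.0% for the chi-square test, against 4.9%, 5.0% and 5.1% for a stratified (Cochran-Mantel-Haenszel) test.
- Over all allocations error is 5.3% against 4.9-5.0%. Power for a 20-point effect (control rate 50%) is 40% in all three cases, against 39%, 40% and 42%.

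Both approaches show the same pattern.

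**The case against.** Randomization already protects the planned tests: their error is about 5% over all allocations, and the confidence interval allows for chance imbalance. The shift is smaller than sampling error, the precision gain is slight, and the documents give no figure for how well either index predicts post-discharge complications. By-group summaries would let a reader see an imbalance. This is a pilot, and complications are one of five aims. All of that stands, and it sets the severity.

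It does not remove the gap. Displaying an imbalance does not correct for it, and an undefined model leaves the choice of covariates open until the data are known.

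A reader might go further than the documents allow in four ways:
- **That the unadjusted tests are invalid or biased.** They are not; the excess error is conditional on an unlucky allocation.
- **That any imbalance passes in full into the complication result.** Only imbalance multiplied by prognostic strength does.
- **That the plan rules out adjustment.** It promises model estimates and leaves their content open.
- **That these two indices are the only baseline information for complications.** Age, sex, health history, LVAD indication, device model and site are also recorded, as are baseline scale scores. The two indices are a reasonable choice because the plan presents them as risk and comorbidity summaries, but they are not the only one.

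**Conclusion.** The point holds as a minor improvement, not as an error that invalidates the planned tests. Two risk measures are collected, allocation is not described as stratified on either, and no named analysis uses them. What adjustment buys is protection in the less lucky allocations. That protection is worth having if the index is strongly prognostic (about 1.6-fold per SD) and small if it is weak (about 1.3-fold). Only about 4% of allocations exceed 0.5 SD on a given index, which is where unadjusted error reaches about 10%.

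The conclusion rests on an inferred 34 per arm and on assumed prognostic strength, event rates and complete follow-up. None of these is given in the documents.

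**What to change.** In Data Analysis, state what the model estimates are for complications (aim 3) and, as a supporting outcome, for unplanned hospitalization:

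- **Outcome.** Per-patient event count over 6 months, or any event by logistic model. Choose one in advance and say which recorded events count.
- **Terms.** Arm plus the Charlson index as a continuous covariate. Add INTERMACS profile only if total events, pooled over arms, reach a threshold fixed beforehand. The documents offer no event rate from which to derive that threshold, so the trial statistician must set it without sight of the arms.
- **Reporting.** Give the adjusted estimate with its 95% confidence interval beside the unadjusted result. The document is written in the past tense, so if arm-level data have already been seen, label the adjusted result post hoc.

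The cost is a few sentences of plan text and a few lines of SAS, with no new data. The downside is one or two degrees of freedom, and little gain if the indices predict these events weakly.

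### Complications and readmissions are recorded monthly as frequencies, but the plan names only per-period tests; one 6-month rate ratio would give the planning estimate the pilot needs

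*Combined protocol and SAP*

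**What the plan says.** - **Purpose.** The pilot seeks preliminary efficacy data. Complications are the third of five listed effects: "3) complications; (4) overall health status, and (5) quality of life". Readmission is not named there.
- **Complications and Hospital Readmission** (under Data Collection). Two forms are used for "capturing characteristics and frequency of LVAD-related complications and unplanned hospitalization through a monthly review". The format is described as a common one for collecting complications and "healthcare utilization/hospital readmission episodes in heart failure".
- **Data Collection.** The time points are "baseline (1-2 days before hospital discharge) and 1, 3, and 6 months after implantation hospitalization discharge". The post-discharge intervals are therefore 1, 2 and 3 months long.
- **Data Analysis.** Outcomes are "compared for each period (T0, T1, T2, and T3) with Mann Whitney U tests and chi-square tests" at the 0.05 level. The section also promises group summaries with 95% confidence intervals and "model estimates and effect size estimates for the next stage of this pilot", without saying which model or which effect size.
- **Sample and Setting; Randomization.** There are 68 patients allocated 1:1, so about 34 per arm. No power or precision basis is given.

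No section says whether a count at T1, T2 or T3 covers the time since the previous visit or all time since discharge. None says whether the unit is any event or the number of events, or when observation ends for a patient who dies, is transplanted or withdraws.

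**The concern.** The data captured are richer than the comparisons named for them. A Mann-Whitney test on counts gives a p-value, not a rate or a ratio of rates. A chi-square test on any event treats a patient with four readmissions like a patient with one. If counts are separate by interval, each test uses one, two or three months of a six-month follow-up. T0 falls before discharge and so cannot contain a post-discharge event, which means the per-period template does not fit these outcomes at that point.

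What is at stake is the figure carried to the next stage. A trial with event counts as an outcome is planned from a control event rate, a dispersion and a plausible rate ratio. As written, analysts could report one period, any-event percentages or a 6-month total from the same data, all within the plan and with different precision.

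**Working it through.** The plan states no power, event rate or expected count, so there is no figure of its own to reproduce. What follows is illustrative.

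**Inputs from the documents:** 68 patients, 1:1, so n = 34 per arm; intervals of 1, 2 and 3 months; alpha 0.05 (taken as two-sided).

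**Inputs assumed:** control rate 0.083 to 0.4 events per patient-month (0.083 × 6 = 0.5 to 0.4 × 6 = 2.4 per patient over six months); gamma-Poisson dispersion k = 0.7; true rate ratio 0.5; 2% monthly exit in both arms.

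**Step 1. Precision with full follow-up.** With control mean m and intervention mean m/2 over the window,

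SE(log rate ratio) = √[1/(34m) + 1/(34m/2) + 2k/34], where 2k/34 = 1.4/34 = 0.0412.

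| Rate | Window | m | Sum under root | SE |
|---|---|---|---|---|
| 0.083 | 6 months | 0.498 | 0.0591 + 0.1181 + 0.0412 = 0.2184 | 0.467 |
| 0.083 | months 3-6 | 0.249 | 0.1181 + 0.2362 + 0.0412 = 0.3955 | 0.629 |
| 0.4 | 6 months | 2.4 | 0.0123 + 0.0245 + 0.0412 = 0.0779 | 0.279 |
| 0.4 | months 3-6 | 1.2 | 0.0245 + 0.0490 + 0.0412 = 0.1147 | 0.339 |

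Using months 3-6 alone inflates the SE by 0.629/0.467 = 1.35 at the low rate and 0.339/0.279 = 1.21 at the high rate.

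The ratio of the upper to the lower 95% limit over six months is exp(2 × 1.997 × SE): about 6.5 at the low rate and 3.0 at the high rate. Simulation with exit and a small-sample robust variance gives 7.1 and 3.1. For an estimate of 0.5, those are intervals of 0.5 divided and multiplied by √7.1 = 2.66 (0.19 to 1.33), or by √3.1 = 1.76 (0.28 to 0.88).

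**Step 2. Power by simulation** (separate runs agree to within about two points):

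| Comparison | 0.083 per month | 0.4 per month |
|---|---|---|
| Mann-Whitney, months 3-6 only | 16% | 39% |
| Mann-Whitney, 6-month total | 26% | 55% |
| 6-month rate test with offset | 28% | 67% |

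At 0.4 per month, the T1 and T2 interval counts give about 25% and 35%, and chi-square on any event by six months gives 34%. Across a wider grid (rates 0.083 to 0.6, dispersion 0.3 to 1.0), the type I error of the rate test is 4.2-5.9%.

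**Step 3. Which reading drives the contrast.**
- Separate counts: at 0.4 per month the best single period has 39% against 67%, a gap of 28 points.
- Cumulative counts: the T3 Mann-Whitney test already uses six months. The gap is 67 − 55 = 12 points at 0.4 per month and 28 − 26 = 2 points at 0.083.

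**Step 4. Time at risk.** With equal exit, the offset changes power by −0.1 to +1.9 points over the wider grid. With an assumed six-month exit of 10% v 25% and no true effect, the rate ratio reads 0.91-0.92 (1.09-1.10 if reversed) when everyone is credited with six months, and 0.99-1.01 with the offset.

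**The case against.** The strongest reply is that the plan leaves room for what is asked. It promises model and effect size estimates, so a reader who infers that a rate model is excluded goes too far: none is named, but none is ruled out. It also promises summaries with confidence intervals. Means and SDs of 6-month counts, if reported, would give an event rate and a rough dispersion. Monthly capture means no information is lost. This stands, and it limits the point to an unspecified analysis. It does not close the gap, because the counting window, the unit and the effect measure all remain open.

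Four further limits stand:
- A reader might infer that the plan discards half the follow-up. That needs separate-interval counts, which no section states.
- Repeat episodes are inferred from the plan's wording about frequency and episodes; they are not stated outright. Nor does any section say that events will be reduced to yes or no.
- The lack of a named model, and the repeated testing over periods, apply to every outcome. What is particular to events is the counting window, time at risk and repeat episodes.
- Rates, dispersion, exit and effect size are all assumed. A smaller effect shrinks the power argument: at rate ratio 0.7 the gain over a 6-month Mann-Whitney test is 0 to 6 points across the wider grid.

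**Conclusion.** The point holds as a worthwhile, low-cost improvement. The named comparisons yield no event-rate effect estimate for complications or readmissions, and one 6-month rate ratio with its interval serves the pilot's purpose better on data already captured. The power gain is large only if counts are separate by interval. Against a cumulative Mann-Whitney test it is modest at 0.4 events per month and close to nil at 0.083. The case therefore rests mainly on obtaining a defined rate, dispersion and rate ratio for the next stage.

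A reader might take this as a threat to the trial's conclusions. The documents do not support that: this is a pilot for preliminary efficacy data with no stated primary outcome, and complications are one of five listed effects. The likely harm is an imprecise or loosely defined planning figure, not a false confirmatory claim. Bias from unequal time at risk is possible, but the documents give no exit figures by which to judge it.

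**What to change.** For complications and for readmissions separately:

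- Make the main result a single 6-month rate ratio with 95% CI, from a count model of events from discharge to month 6 with arm as a term and log(months observed) as offset.
- Allow for overdispersion, either by Poisson with a small-sample robust variance or by negative binomial. Either is acceptable: in a 2,000-trial check at 0.4 events per month, type I error was 5.6% for the robust rate test and 6.0-6.5% for negative binomial.
- End observation at death, transplant or withdrawal. Report event rate and dispersion by arm, with deaths and transplants tabulated alongside.
- Show T1, T2 and T3 counts descriptively, stating whether each is for the interval or cumulative. Drop any T0 test of post-discharge events.
- The document is written largely in the past tense. If results are already known, label this analysis post hoc.

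The cost is a few sentences and one SAS model per outcome. Exit dates are needed. The model assumes that exit is non-informative, the variance is estimated from only 68 patients, and at low event rates the return is the estimate and its interval rather than extra power.

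### The complication and readmission comparison does not provide for death, transplant or device removal and makes no allowance for time at risk, so early deaths can distort it in either direction

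*Combined protocol and SAP*

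**What the plan says.** The Purpose section lists complications among five effects of the app; the study is to "evaluate the effects of the app on the patient's (1) self-efficacy and (2) adherence to the LVAD care regimen; (3) complications", followed by health status and quality of life.

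Under Data Collection, the item on complications and readmission describes two forms for "capturing characteristics and frequency of LVAD-related complications and unplanned hospitalization". The information comes "through a monthly review of the patient's medical record(s) and interviews of patients and/or caregivers". On the content of the forms it says only this: "These forms consisted of a checklist and tables format". The checklist items are not listed.

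Data Analysis gives one rule for all outcomes: "Differences in the study group's outcome variables were compared for each period (T0, T1, T2, and T3"), using "Mann Whitney U tests and chi-square tests set at 0.05 level of significance". It does not say which test goes with which outcome, or whether event counts are cumulative or per interval.

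The aims, the outcome descriptions and the analysis do not mention a participant's death, survival, transplant, device removal, censoring, person-time or competing risks. Mortality appears only in the title of a cited reference.

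**The concern.** The outcome is a frequency collected over six months after discharge in patients with newly implanted devices. A frequency can be read only against the time over which it could accrue. A patient who dies at the end of month 2 has been observed for 2/6, or one third, of the window. If that patient had no admission and no complication entry, the forms as described hold a zero. The analysis section has no step that separates this zero from that of a patient who completed six uneventful months on support. Transplant and device removal shorten the count in the same way.

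Two things are at stake. First, a lower complication or readmission count in one arm could reflect less time at risk and not better self-management. Second, the app directs daily device care and routes abnormal results to nurses, so an effect on survival in either direction is conceivable, and the planned comparison would not show it. Data Analysis also says that effect sizes from this pilot are to inform the next stage, so a distorted estimate would carry forward.

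**Working it through.** **No figure to reproduce.** The documents give no event rate, death rate, dropout rate or derivation of the sample size. All rates below are assumptions for illustration.

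**Inputs from the documents.** 68 patients (Sample and Setting); 1:1 allocation (Randomization); follow-up to 6 months after discharge (Data Collection). Arm sizes are not stated, so 68/2 = 34 per arm is assumed.

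**Step 1: ceiling per death.** One patient is 1/34 = 2.9 percentage points of an arm's proportion. For the outcome as described, scoring a death as event-free costs the full 2.9 points only if that patient would certainly have had a listed event later. If the chance of a later event were 50%, the cost would be 0.5/34 = 1.5 points.

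**Step 2: a worked example.** Assume constant, independent monthly hazards: the same complication hazard *e* in both arms, and a death hazard *d* that differs.

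- Complication risk of 50% over 6 months: *e* = -ln(0.5)/6 = 0.1155
- Deaths of 5%: *d* = -ln(0.95)/6 = 0.0085
- Deaths of 20%: *d* = -ln(0.80)/6 = 0.0372

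Probability that a complication is seen before death: *e*/(*e*+*d*) × (1 - exp(-6(*e*+*d*))).

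- 5% arm: 0.9311 × 0.525 = 48.9%
- 20% arm: 0.7565 × 0.600 = 45.4%

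Probability of dying with no complication first:

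- 5% arm: 52.5 - 48.9 = 3.6%, about 1.2 patients of 34
- 20% arm: 60.0 - 45.4 = 14.6%, about 5.0 patients of 34

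**Step 3: the same data under three handlings.**

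| Handling of a death without a complication | 5% deaths | 20% deaths | Arm with more deaths looks |
|---|---|---|---|
| Counted as event-free | 48.9% | 45.4% | 3.5 points better |
| Patient dropped | 0.4888/(1 - 0.0362) = 50.7% | 0.4539/(1 - 0.1461) = 53.2% | about 2.4 points worse |
| Death counted as an event | 1 - 0.5×0.95 = 52.5% | 1 - 0.5×0.80 = 60.0% | 7.5 points worse |

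The assumed mortality difference is 20 - 5 = 15 points. The first two handlings do not show it, and they differ in sign. The composite gets the direction right but shows only half the size.

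**Step 4: range under the event-free handling.** Apparent advantage of the arm with more deaths, for complication risks of 30%, 50% and 70%:

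- Deaths 5% vs 20%, constant hazards: 2.2, 3.5 and 4.5 points (0.8 to 1.5 patients of 34).
- Deaths 5% vs 20%, all at the very start: 4.5, 7.5 and 10.5 points.
- Deaths 5% vs 10%: 0.7 to 1.5 points across the three risks, or 1.5 to 3.5 if all are immediate.

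**Step 5: does person-time remove the distortion?** Mean months to first complication, death or month 6 = (1 - exp(-6(*e*+*d*)))/(*e*+*d*).

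- 5% arm: 0.525/0.1241 = 4.23 months; rate 0.4888/4.23 = 0.1155 per month
- 20% arm: 0.600/0.1527 = 3.93 months; rate 0.4539/3.93 = 0.1155 per month

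The rates agree, as they should when the complication hazard is the same in both arms. They say nothing about death, which has to be reported separately.

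**The case against.** Much of the case on the other side stands.

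- **The plan is silent on how deaths are scored.** A reader might infer that a patient who dies is scored as event-free, so that the arm with more deaths will look safer. No sentence says so. A patient who died before a visit could equally drop out of that visit's denominator, which reverses the direction in the example. The direction is therefore conditional. The silence is still a defect, because the sign depends on a rule that could be chosen after the data are seen.
- **The form items are not shown.** A reader might infer that deaths went unrecorded. The documents do not support this: a fatal outcome could be entered as a characteristic of a complication, and monthly record review with caregiver interviews would probably reveal a death. But a fatal device-related complication does not cover death from another or unknown cause, and no outcome or analysis uses a death that was found.
- **This is not called a safety outcome.** Correct. Complications are one of five effects in a pilot seeking preliminary efficacy data, and no six-month binary endpoint is defined. The point concerns the complication and readmission outcome under its own name.
- **The distortion is small beside the noise.** About 34 per arm gives 80% power only for a drop of roughly 32 points from 50% (two-sided 0.05), so a 3.5-point shift would seldom decide a test. That is fair for the tests. It is weaker for the effect estimates, which are meant to be carried forward.
- **A composite changes the aim.** Also fair, and it is a reason not to make a composite the sole definition.

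**Conclusion.** The gap is real. As described, the outcome covers device-related complications and unplanned admissions. Death from any cause, transplant and device removal are neither events nor ends of follow-up, and the comparison at fixed periods ignores time at risk. The complication and readmission comparison can therefore be distorted when deaths differ between arms, and it would not show that they differ.

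The size rests on assumptions: 34 per arm, the event and death rates, and independent hazards. Each death without a listed event moves an arm's proportion by at most 2.9 points. In the 50% example with deaths of 5% and 20%, the arm with more deaths looks 3.5 points better if deaths count as event-free and about 2.4 points worse if those patients are dropped. The documents do not support a claim that the plan favours the arm with more deaths, or any fixed figure for the bias. This should be corrected before the complication results are interpreted or used for planning, but it does not by itself invalidate the pilot.

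**What to change.** 1. From the medical records already reviewed monthly, record the date of death from any cause and the date of transplant or device removal. The document is written largely in the past tense, so this may mean going back to the records.
2. Report deaths by arm beside complications and readmissions, whatever else is done.
3. Compare complications and readmissions as events per person-month on LVAD support, ending each patient's time at death, transplant, device removal or month 6. State this rule in Data Analysis.
4. Add a supportive analysis of death, complication or unplanned hospitalization as a composite, with each component shown by arm.

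The cost is a few data fields, some record retrieval and a short addition to Data Analysis. The composite mixes events of different weight and can dilute a mortality difference, so it should not stand without its components. A single rate per person-month also averages over any change in risk after discharge; with unequal early deaths, rates by period are a useful check.
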